Physical performance: running speed, HR range and distance that have been ran for the 30 minutes of exercise will be collected during exercise.

tDCS Adverse Effects Questionnaire: At the end of each stimulation session, subjects will complete a 5-point scale questionnaire that evaluates potential common adverse effects of tDCS (headache, neck pain, scalp pain, scalp burning sensation, tingling, skin redness, sleepiness, concentration, and acute mood change).

Exercise Adverse Effects: During each AE session, subjects will be monitored (HR variability). The session will be stopped if the HR is superior to 80% of HRmax [36], or if the patient presents any signs of discomfort. Also if the subject requests, the intensity can be reduced up to 50% of HR max or the duration can be reduced up to 15min. To evaluate the adverse effects of AE during the training, we will record any musculoskeletal symptoms, such as pain, fatigue, tingling or cardiovascular symptoms, such as shortness of breath [29]. As recommended by the ACSM guidelines for AE in patients with FM, we will monitor the level of pain and fatigue continuously throughout the tests using the VAS. We will also follow the emergency procedure guidelines from the ACSM.

If a subject is not comfortable to perform one of the described assessments, we will make a note in the study binder and proceed to the next one.

VIII. BIOSTATISTICAL ANALYSIS

Sample Size Calculation: This study's original sample size calculation was based on an expected effect size of 0.78, with 85% statistical power and a significance level of 0.05. However, after 6 years of the original sample size calculation (it was done in 2017 upon grant submission, see appendix 2), we have observed in our recent study in collaboration with other colleagues and recent meta-analyses effect sizes ranging from 0.9 to 1.26, which are larger than we initially anticipated. Considering this new information, we re-estimated the sample size to ensure we do not expose subjects to the burden of participating in a study that involves a placebo arm. Also, this would make the study feasible to be completed in the 5-year period of this grant, given our recruitment was significantly affected by the COVID pandemic, especially in the years 2020 and 2021. We have recalculated the sample size using the smallest reported effect size (0.90) using the t-test calculation for the difference between two independent means (to test for the main hypothesis) – this is the same method used in the original sample size calculation; and determined that we need a total of 116 participants (29 in each group) to achieve 85% power (as planned before). We assumed a type I error of 5% (alpha), and a type 2 error of 15% (beta). We also made this calculation considering the same parameters used in the original sample size calculation, such as dropout rates of 20%. The sensitivity analysis for the sample size calculation is summarized in the table below.

[figure not shown]
Therefore, we reduced the sample size from 148 to 116 participants, which will maintain the same planned statistical power (85%). This revised sample size will allow us to detect the more precise effect sizes currently reported in the literature and will also make the study feasible to be completed on time, given the large impact of the COVID pandemic on our study.

[figure not shown]
Planned Analysis:

The primary analysis: All the analyses will be performed as intention-to-treat in which all subjects undergoing randomization who receive at least one intervention session (randomization will take place immediately before the first intervention) will be included. We will conduct sensitivity analyses and test different models of handling missing data (LOFC and MI). The change in the primary efficacy endpoint, CPM (and also TSPS), from baseline to week 4 will be tested with a mixed linear model. This model will be adjusted for important demographic variables (i.e., gender) and also baseline clinical parameters where appropriate. All tests will be two-sided (alpha level, 0.05). We will initially test our main hypothesis that the combined treatment induces a greater increase in CPM (and decrease in TSPS) as compared to the control condition. If the effect is significant, we will then test differences between the combined group vs these two interventions alone.

[figure not shown]
In order to understand the time effect of this intervention (using the secondary endpoints added in this model (week1 and follow-up)), we will run a secondary mixed linear model to estimate the rate of change over time by also including an interaction between treatment and time as to detect whether treatment effect changes differently according time. If the interaction is not significant we will then test whether there is a main effect of time that is independent of treatment level (interaction will be then removed from the model). We will adjust this model for important covariates such as age, gender, pain levels (numeric pain scale – NPS), and other baseline clinical outcomes where appropriate. For the secondary clinical variables with a significant effect we will also test whether they moderate the interventions' effects on our mechanistic outcomes, thereby gaining additional mechanistic insights.

To complete our analysis, we will apply a path analysis [1, 2] to the outcome data (CPM and TSPS) to determine if endogenous pain modulation changes (as indexed by CPM and TSPS) associated with the combined intervention (tDCS and AE) is related to direct effects versus indirect effects through improvements in secondary outcomes. We propose that a direct effect of tDCS and AE on the endogenous pain inhibitory system can be inferred if the treatment effect cannot be explained by changes in psychological or functional outcomes.

[figure not shown]

[figure not shown]
Detailed Protocol 23

[figure not shown]
Detailed Protocol 24

[figure not shown]
Detailed Protocol 25

[figure not shown]
Detailed Protocol 26

[figure not shown]
Detailed Protocol 27

[figure not shown]
Detailed Protocol 28

[figure not shown]
Detailed Protocol 29

[figure not shown]
Detailed Protocol 30

[figure not shown]
Detailed Protocol 31

Detailed Protocol 32

Detailed Protocol 33

Detailed Protocol 34

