Aim 2: Determine the effect of these interventions on cortical markers of inhibitory control that are also affected in FM, such as intracortical inhibition as assessed by transcranial magnetic stimulation (TMS) and changes in thalamocortical dysrhythmia as assessed by EEG. *We hypothesize that active tDCS combined with exercise will result in greater increases in intracortical inhibition as measured by the short intracortical inhibition (SICI). These increases will be associated with greater reduction of pain when compared to either intervention alone. We also hypothesize that tDCS combined with exercise will induce a greater decrease in theta power than any intervention alone, as well as to the control group. Therefore, we hypothesize that decreases in theta EEG band power could be used as a marker of the normalization of the thalamic dysrhythmia normalization.*

Aim 3: Assess the number of sessions needed to induce significant changes in markers of endogenous pain inhibitory system and central sensitization (CPM and TSPS) and cortical changes (as indexed by paired pulse TMS and EEG). *We hypothesize that the group receiving the top-down and bottom-up strategies (tDCS and AE) will have a greater number of subjects with target engagement (change of at least 30% as compared to baseline) of pain and cortical marker.*

Sub-aim 3: Assess whether engagement of the two main targets tested in this study – TSPS and CPM – are associated with the secondary clinical outcomes (i.e., changes in pain outcomes: Brief Pain Inventory, Revised Fibromyalgia Impact Questionnaire). *We hypothesize that changes in TSPS and CPM will be correlated with these pain outcomes. We also hypothesize to find a correlation between baseline values of TSPS and CPM and pain relief immediately after the intervention.* This result will be important as to assess the suitability of such markers as potential treatment response predictors.

[figure not shown]
III MEDICAL MONITOR

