- 7) current opiate use in large doses (more than 30mg of oxycodone/hydrocodone or 7.5mg of hydromorphone (Dilaudid) or equivalent),
- 8) Patients will be excluded when they have increased risk for exercise as defined as (i) not fulfilling the american college of sports medicine (acsm) criteria (i.e., risk of cardiovascular complication [30]) and in this case not cleared by a licensed physician.

[figure not shown]
[figure not shown]
[figure not shown]
(If a patient meets the inclusion criteria but is found to have a risk factor (according to the ACSM guidelines), he/she will undergo a medical visit in order to obtain clearance. If he/she does not pass the medical clearance, he/she will not be included in the study.

[figure not shown]
V. SUBJECT ENROLLMENT

Subjects will be sought through the following sources:

- Attending physicians, therapists, clinicians and other healthcare providers may refer out subjects to the study.
- We will provide them with study information sheets and flyers. Prospective subjects will be encouraged to contact the study co-investigators.
- Flyers posted in the outpatient specialist clinics and public posting boards (i.e., digital signage).
- Internet (i.e., Google Ads) and newspaper advertisements.
- Advertisings posted in public transportation (The T).
- Via the Partners Healthcare Research Patient Data Registry (RPDR), Patient Gateway, and Research Match (Vanderbilt Recruitment Tool).
- Potential subjects might also be identified through their medical records (epic LMR, etc.) and their physicians might be asked to inform the subjects about the study.
- Support groups presentations.

Detailed Protocol 7

The method of randomization is a 1:1:1:1 permuted block randomization, generated by a web-based randomization tool. Randomization order will be kept in individual sealed and opaque envelopes with order of entrance and the randomization master list will be kept in a locked drawer; therefore, subjects will get their assignment according to the order of entrance in the study.

[figure not shown]

Figure 1 - Intervention groups with 1:1:1:1 allocation ratio.

Blinding Procedure:

Participants, family members, treating staff/ physicians, data collectors, site investigators and the statistician will be blinded to group stimulation assignment.

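### Aim 3's only stated hypothesis counts subjects past a 30% change in continuous markers; a full-scale comparison by visit would be more sensitive, and none is tied to this aim

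*Combined protocol and SAP*

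**What the plan says.** Aim 3 (II. Specific Aims) asks how many sessions it takes to produce a significant change in CPM, TSPS, paired-pulse TMS and EEG. Its one stated hypothesis is that the group receiving both tDCS and aerobic exercise "will have a greater number of subjects with target engagement (change of at least 30% as compared to baseline".

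Section VII and the Aims measure every one of these markers on a continuous scale. TSPS is the 15th-stimulus rating minus the first. CPM is a difference between two mean ratings. SICI and ICF are percentages of inhibition or facilitation. The EEG marker is theta band power.

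Elsewhere the plan keeps the full scale. In Section VIII, Planned Analysis, the week-4 change in CPM and TSPS "will be tested with a mixed linear model". A secondary mixed model with a treatment-by-time term follows, with week 1 and follow-up as its added endpoints. Aim 2 words its SICI and theta hypotheses as greater increases or decreases, with no cut.

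The sample size was obtained "using the smallest reported effect size (0.90) using the t-test calculation for the difference between two independent means", for the main hypothesis.

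**The concern.** Reducing a continuous change to reached or did not reach 30% discards information, however well the cut is defined. The readable text gives no reason for choosing 30%, names no test or visit for the count, and does not size the trial for a comparison of proportions.

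The loss matters more for Aim 3 than for a plain efficacy question, because the aim asks when a change becomes detectable. If arms are compared on the count, a real difference may be missed, or may appear at a later visit than the same data would show on the full scale.

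The continuous models in Section VIII do not clearly fill the gap. The primary model concerns week 4. The time-course model does not name visits 11 and 14, although the visit description has CPM and TSPS collected there during the stimulation course. Neither model names TMS or EEG, so for those markers the 30% count is the only between-arm comparison stated under Aim 3.

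**Working it through.** **Inputs from the documents**
- Effect size 0.90, two-group t-test (Section VIII, Sample Size Calculation).
- Error rates: "We assumed a type I error of 5% (alpha), and a type 2 error of 15% (beta"; sidedness: "All tests will be two-sided (alpha level, 0.05".
- Sample size: "we need a total of 116 participants (29 in each group) to achieve 85% power (as planned before".
- Dropout 20%: "such as dropout rates of 20" per cent.
- Equal arms: "The method of randomization is a 1:1:1:1 permuted block randomization".

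**Assumptions not in the documents:** normally distributed changes, equal SD in both arms, and one common cut on the change score.

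**Step 1: reproduce the plan's figure.** Normal approximation: n = 2(1.960 + 1.036)²/0.90² = 2 × 8.978/0.81 = 22.2, so 23 per arm. Then 23/0.8 = 28.75, so 29 per arm, and 4 × 29 = 116. This matches. The exact t-test gives 23.2, rounded up to 24; 24 × 1.2 = 28.8 also leads to 29. I therefore show 23 and 24 evaluable, and 29 in case everyone is analysed.

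**Step 2: full-scale power.** From the noncentral t distribution at d = 0.90, two-sided 0.05: 84.7% (n = 23), 86.3% (n = 24), 92.0% (n = 29).

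**Step 3: responder-count power.** If a proportion p0 of controls passes the cut, the combined-arm proportion is p1 = Φ(0.90 + Φ⁻¹(p0)). A search over all cut positions puts the best one midway between the arm means, at 0.45 SD: p1 = Φ(0.45) = 67.4% and p0 = 1 − 67.4% = 32.6%. With p0 = 10%, p1 = Φ(0.90 − 1.282) = 35.1%. Power is by exact enumeration of two binomials.

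| Evaluable per arm | Full scale | Best cut: chi-square / Fisher | 10% of controls engaged: chi-square / Fisher |
|---|---|---|---|
| 23 | 84.7% | 68.5% / 56.8% | 56.0% / 43.7% |
| 24 | 86.3% | 71.8% / 60.8% | 58.3% / 46.2% |
| 29 | 92.0% | 76.7% / 67.5% | 64.6% / 52.6% |

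At the best cut the loss is 14.5 to 16.2 points by chi-square and 24.5 to 27.9 points by Fisher.

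**Step 4: the same loss as a sample size.** The pooled two-proportion formula at the best cut, for 85% power, gives n = [1.960√(2 × 0.5 × 0.5) + 1.036√(2 × 0.674 × 0.326)]²/(0.674 − 0.326)², which is about 35.6, so 36 evaluable per arm. Then 36/0.8 = 45 per arm, or 180 in total, against 116. This only shows scale; no increase is suggested.

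**Step 5: where the markers are collected** (visit description). CPM and TSPS after the start of stimulation: visits 6, 11, 14, 17 and 18. TMS and EEG: visits 11, 17 and 18, not 6 or 14.

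**The case against.** The strongest reply is that the plan does not rely on the count. The treatment-by-time model is a full-scale analysis of time course and addresses much the same question as Aim 3. Aim 2 treats SICI and theta power as measured changes, and Sub-aim 3 correlates changes in TSPS and CPM with clinical outcomes. This stands. A reader might infer that the trial analyses these markers only as responders, and the documents do not support that. What remains is narrower: the time model is not tied to Aim 3, leaves mid-course visits unnamed and omits TMS and EEG.

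Second, the 85% belongs to the main hypothesis. No power is claimed for Aim 3, and d = 0.90 is not given for TMS or EEG. It would be wrong to read the table as a fall from a planned Aim 3 power, and it is offered only as a benchmark. Nor is 69% a ceiling: it needs 23 evaluable per arm, and the figure is higher with 24 or 29. The plan's intention-to-treat analysis, with missing-data models to be tested, means that completers need not be the analysis set.

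Third, the protocol's cut is relative to each subject's own baseline, so the absolute cut varies between subjects. Responder rates and SDs are not given. The calculation therefore does not model the 30% rule itself. This stands as a limit on the figures.

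Fourth, a reader might conclude that Aim 3 will overstate the sessions needed. That requires an assumed build-up of effect over visits, and a rule that between-arm significance at each visit decides the answer. The documents give neither.

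Finally, a count of engaged subjects answers a legitimate question of its own, Aim 3 is not primary, and Section VII calls the EEG exploratory. These points argue for keeping the count as a display and for modest severity. They do not make it the more sensitive comparison. Some figures and an appendix are not shown, so nothing is inferred from their absence.

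**Conclusion.** The point holds as a worthwhile, inexpensive improvement to a non-primary aim. Aim 3's only stated hypothesis is a responder count on continuous markers, and no full-scale comparison by visit is assigned to that aim.

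Under normal changes, equal SD, a common cut and d = 0.90, the count costs roughly 15 power points or more even with the cut ideally placed, and more if few controls respond. The effect on the sessions question is a risk of missed or later detection; its size cannot be derived from the documents. The primary analysis and its stated 85% power are unaffected.

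**What to change.** In Aim 3 and in Section VIII, Planned Analysis, state that the between-arm comparison for Aim 3 uses the continuous change in each marker, adjusted for that marker's baseline value. Report the arm difference with its 95% CI at each visit where the marker is collected: CPM and TSPS at visits 6, 11, 14, 17 and 18; TMS and EEG at visits 11, 17 and 18. Do this by extending the existing treatment-by-time mixed model to those visits and to TMS and EEG. Keep the number of subjects with at least 30% change as a descriptive display by arm and visit.

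The cost is a few sentences, with no new data or participants. The small downside is that the Aim 3 headline becomes a mean difference rather than a responder count.

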Chronic pain results from an imbalance between excitatory and inhibitory pain pathways. Recent evidence has suggested that pain inhibitory pathways are affected in FM; thus, further understanding these pathways' role in FM can significantly change how FM is treated. Two assessments can test pain inhibitory activity: Temporal Slow Pain Summation (TSPS) and

conditioned pain modulation (CPM). During TSPS, the progressive increase in pain intensity following repetition of identical nociceptive stimuli reflects C-fiber and other central neurons temporal summation and has been used as a marker for pain sensitivity. TSPS does not seem dependent on increased impulse C-fiber input, suggesting that TSPS is a CNS phenomenon rather than peripheral [8]. As a CNS phenomenon, several mechanisms contribute to TSPS, including ineffective central pain modulation [9] and rostral ventromedial medulla facilitation [10]. Moreover, TSPS is thought to rely on the same mechanisms that underline the initiation and maintenance of several chronic pain conditions, and thus TSPS has also been widely studied in FM [11, 12]. FM patients also demonstrate lower CPM inhibitory efficacy. Indeed, the rate of patients with FM reporting pain facilitation during CPM has been found to be significantly increased compared with that of the controls (41.7% vs 21.2%) [13]. Based on the current literature, there is strong evidence that for some FM patients the endogenous pain regulatory system is impaired. Moreover, CPM efficacy has already been related to pain development 6 months after surgery [14], making it another suitable marker for response prediction.

There is also evidence of CNS changes in FM that are associated with a deficit in the inhibitory control, namely abnormal cortical excitability as expressed by decreased short intracortical inhibition (SICI) and facilitation (SICF) and increased resting motor threshold [15]. This is thought to reflect an inhibitory deficit that is associated with altered thalamic anatomy and activity [16], which may result in abnormal thalamocortical circuits, as evidenced by the association between central pain and thalamic dysrhythmia [17-19]. Therefore, the unravelling of inhibitory deficits underlying pain maintenance mechanisms in patients with FM can also help the development of novel interventions for this pathology, as well as for other chronic pain conditions associated with a deficit in the regulatory pain system.

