The overall goal of this project is to investigate the mechanisms of optimized tDCS via two important markers of chronic pain, conditioning pain modulation (CPM) and slow temporal summation (STS). In addition, the results of this study will represent a significant step toward developing a novel low-cost therapy for FM and validating a therapeutic novel target.

Sponsors

This study is funded by NIH-NCCIH (1 R01 AT009491-01A1).

II. SPECIFIC AIMS

This trial aims at understanding the mechanisms of optimized tDCS (16 tDCS sessions combined with exercise) on pain control. Optimized tDCS can lead to stronger engagement of the endogenous pain regulatory system that will ultimately lead to increased pain relief in patients with FM. Therefore, we designed a 2x2 factorial mechanistic trial [tDCS (active and sham) and aerobic exercise (active and control)] to test the following aims:

Aim 1 (primary outcome): Evaluate the effects of 4 weeks of tDCS coupled with exercise on the endogenous pain regulatory system assessed by CPM and central sensitization as assessed by TSPS, and compared to either intervention alone and to no intervention. *We hypothesize that tDCS coupled with exercise will result in restoration of pain endogenous regulatory system as indexed by greater decrease in SPS and increase in CPM responses. We also hypothesize to observe differences between groups as exercises may have a larger effect on the insula and somatosensory cortex (which is indexed by SPS) while tDCS seems to have a greater effect on prefrontal and*

cingulate cortex (which is indexed by CPM). Thus, these markers will be important to understand to what extend the nodes of pain matrix may be more involved in pain relief and whether the effects of tDCS and exercises are mainly mediated by an increase in inhibition (increase of CPM) or a decrease of excitation (decrease of TSPS).

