**Visits 0 and 1 may be completed in the same day or broken up into two separate visits as the subject prefers*

Daily pain reports will be collected for the two weeks between V1 and V2.

VISITS 1.1 – 1.3: Subjects will be randomized during visit 1.1. The two groups will participate in a different conditioning exercise program for two weeks according to their group assignment (see section VI). At visits 1.1, we will conduct assessments of pain, quality of life, TPSP, CPM, TMS and EEG acquisition (we will offer the possibility of splitting this visit into two visits if the subject gets too tired). At visit 1.3, we will conduct assessments of pain and quality of life, TPSP and CPM. In all these visits we will conduct AE adverse effects questionnaires.

VISITS 2, 11, 17: assessments of pain (except visit 2), quality of life (except visit 2), TSPS, CPM, TMS and EEG acquisition. At the same visit, tDCS and AE will be performed. Also, tDCS and AE adverse effects questionnaire.

VISITS 6 and 14: tDCS, AE, tDCS and AE adverse effects questionnaire, CPM, TSPS, assessments of Pain

[figure not shown]
VISITS 3, 5, 8, 10: tDCS only and tDCS adverse effect questionnaire. The subjects will have the option of choosing to do the visits remotely home-based tDCS (Soterix Medical 1X1 tDCS mini-CT stimulator device), in order to decrease the burn of daily visits at our site.

[figure not shown]
VISITS: 4, 7, 9, 12, 13, 15, 16: tDCS, AE and tDCS and AE adverse effects questionnaire.

VISIT: 18: Pain and quality of life assessments, TMS, EEG, CPM, TSPS.

[figure not shown]
Replacement of missed sessions (though all the effort will be made to avoid missing sessions) will be allowed to up to 20% of missed sessions (up to 4 total visits) according to the treatment schedule. Follow-up and assessments will be encouraged even if more than 20% of missed sessions given data will be analyzed as ITT (though we expect this to be low). We will allow the following visit windows:

- *between visit 1 and 1.1: 2 weeks*
- *between visits during the conditioning period (from visit 1.1 to 1.3): 2 weekdays*
- *between visit 1.3 and visit 2: up to 1 week*
- *between visit 17 and visit 18: up to 2 weeks (before or after the final follow-up, meaning visit 18 could happen 2.5 months to 3.5 months from visit 17)*
- *between Visit 2 and Visit 17: up to 6 weeks*

[figure not shown]

Detailed Protocol 16

Detailed Protocol 17

VII. DESCRIPTION OF ASSESSMENTS

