TSPS Protocol – Heat pulses will be generated by a TSA-II Stimulator (Medoc Advanced Medical Systems, Ramat Yishai, Israel) delivered to the right dominant proximal volar forearm using an appropriate size embedded HP-thermode. We will follow the adapted protocol suggested by [43], in which the HP-thermode was programmed to deliver pulses rising/fall of 1-2-s, depending on subject's heat-evoked pain threshold, from adapting temperatures to peak temperatures, with a plateau of .7-s. Subjects will be trained to determine the temperature necessary to elicit pain-60 (see CPM protocol below) . Subsequently, they will receive 1 train of 15 repetitive heat stimuli at 0.4 Hz to the same area, in which by being suitable for eliciting TSPS in most subjects, allows the rating of individual pain stimuli and is unlikely to induce peripheral sensitization [44]. . TSPS will be calculated as the difference between heat pain rating after the 15th stimulus minus the 1st stimulus.

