CPM Protocol – The protocol involves two conditions, the *test-stimulus* and the *conditioned-stimulus*. We will follow the adapted protocol suggested by Granot, 2008 [84] and Nir, 2011[85]. We will first determine the pain-60 test temperature (which is the temperature that induces pain experience at a magnitude of 60 on a 60-100 NPS) by applying a Peltier thermode (Medoc Advanced Medical Systems, Ramat Yishai, Israel) on the right forearm of subjects and delivering three short heat stimuli (43, 44, and 45 °C), each lasting for 7 s starting from the time the stimulus intensity reaches the destination temperature. Subjects will be asked to rate the level of pain intensity using a numerical pain scale (NPS) ranging from 0 = “no pain” to 100 = “the worst pain imaginable”. If the first temperature of 43 °C is considered too painful (>60), we will stop the series and will provide additional stimuli at lower temperatures of 41 and 42 °C. If the three temperatures of (43, 44, and 45 °C), were not able to achieve pain-60, we will deliver additional stimuli at 46, 47, and 48 °C until the desired pain level of 60 (in the unlikely event that neither of those temperatures were sufficient to elicit pain-60, we will consider it to be 48°C). Once determined the pain-60 temperature, we will administer the test stimulus, applied for 30 s at that temperature and subjects will be asked to rate their levels of pain intensity 3 times: at 10, 20 and 30s after the thermode reaches the pain-60 temperature (mean scores of the the three pain rating will be calculated). Five minutes after delivering the test stimulus, for the *conditioned-stimulus*, the left hand of the subject will be immersed in a bath of water set at 10 to 12°C for 30 seconds. Then, the same pain-60 temperature will be applied on the right forearm of the subject (left hand will still be immersed), for 30 s and subject will again be asked to rate their levels of pain intensity 3 times after the thermode reaches the pain-60 temperature: at 10, 20 and 30s (mean scores of the three pain rating will be calculated). CPM response will be calculated as the difference between the average of pain ratings from the test stimulus minus the average of pain ratings during the conditioned stimulus.

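### Aim 3's 30% engagement rule does not say how to treat negative, zero or near-zero baselines, which CPM, a signed difference score, can produce

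*Combined protocol and SAP*

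**What the plan says.** Section II, Aim 3 covers CPM, TSPS, paired-pulse TMS and EEG, and predicts that the combined arm will show a "greater number of subjects with target engagement (change of at least 30% as compared to baseline) of pain and cortical marker". Aim 3 gives no formula, no direction and no baseline visit.

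Section VII defines the two main markers as differences of pain ratings. For CPM, "CPM response will be calculated as the difference between the average of pain ratings from the test stimulus minus" the average under the conditioned stimulus. Ratings run from 0 to 100, so CPM can lie anywhere from -100 to +100. For the other marker, "TSPS will be calculated as the difference between heat pain rating after the 15th stimulus minus the 1st stimulus".

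Section I cites a study in which the frequency among "patients with FM reporting pain facilitation during CPM has been found to be significantly increased compared with that of the controls (41.7% vs 21.2" per cent). On Section VII's sign convention, facilitation is a negative CPM.

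Direction is stated outside Aim 3. Aim 1 describes restoration "as indexed by greater decrease in SPS and increase in CPM responses", and Aim 2 expects intracortical inhibition to rise and theta power to fall.

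CPM and TSPS are measured three times before or at the start of stimulation. The first is visit 1.1, where randomisation also takes place. Next, "At visit 1.3, we will conduct assessments of pain and quality of life, TPSP and CPM". Visit 2 then includes "quality of life (except visit 2), TSPS, CPM, TMS and EEG acquisition".

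The readable part of Section VIII analyses CPM and TSPS as continuous outcomes and says nothing about engagement.

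**The concern.** A percentage change needs a positive denominator that is not close to zero. CPM does not guarantee one, and the protocol's own background suggests that many of these patients start below zero. Impaired CPM is what the treatment is meant to restore, so the patients of most interest are the ones for whom the rule fails.

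Aim 3 compares the number of engaged patients between arms. If the formula is not fixed, the analyst must choose one when the data are in hand, and the choice can change both who counts and how well the arms separate. The plan should settle this in advance.

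**Working it through.** **The plan's own figure.** No engagement rate, sample size or power is given for the 30% rule. The only computed figure is the sample size in Section VIII, and it reproduces. With effect 0.90, two-sided alpha 0.05 and power 85%, n = 2 x (1.960 + 1.036)^2 / 0.90^2 = 22.2, so 23 per arm; 23 / 0.80 = 28.75, so 29; 29 x 4 = 116. It does not depend on the engagement rule.

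**Arithmetic that needs no assumptions (CPM, b = baseline, f = follow-up).**

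- Reading A, (f - b)/b >= 0.30. From -10 to +5: 15/(-10) = -150%, a clear improvement that is not engaged. From -10 to -14: -4/(-10) = +40%, a worsening that is engaged.
- Reading B, (f - b)/|b| >= 0.30. Direction is right. From +2 to +3: 1/2 = +50%, engaged. From 40 to 51: 11/40 = +27.5%, not engaged.
- Both are undefined at b = 0.

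**How many patients this touches.** If 41.7% start negative, 116 x 0.417 = 48.4 patients; at the cited control rate, 116 x 0.212 = 24.6.

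**Simulation.** Inputs from the documents: 41.7% and 21.2% with negative CPM (Section I); a shift of 0 or 0.90 (Section VIII, taken here as CPM standard deviations); 20% dropout. Assumed: CPM normal, equal variance at both times, baseline to follow-up correlation r = 0.4 to 0.8. Mean/SD is then z(0.583) = 0.21 or z(0.788) = 0.80. There were 2,000,000 pairs per scenario. A directed cut-off, f - b >= 0.5 SD, serves as a comparator only. Power uses the two-proportion normal approximation, two-sided 0.05, with 29 x 0.8 = 23 per arm.

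| Result over r = 0.4-0.8 | 41.7% negative | 21.2% negative |
|---|---|---|
| A and B classify differently | 31-40% | 17-21% |
| Engaged under A, no shift -> 0.90 SD | 26-28% -> 37-46% | 27-29% -> 50-60% |
| Engaged under B, no shift -> 0.90 SD | 36-43% -> 73-84% | 34-41% -> 69-80% |
| Engaged under cut-off, no shift -> 0.90 SD | 21-32% -> 64-74% | 21-32% -> 64-74% |
| Of those engaged under A with no shift, actually worse | 37-41% | 12-19% |
| Power, 23 per arm: A | 13-24% | 31-61% |
| Power, 23 per arm: B | 54-93% | 49-90% |
| Power, 23 per arm: cut-off | 58-97% | 58-97% |

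Example for B at 41.7% and r = 0.6: 40.7% against 76.4% engaged, difference 0.357. The standard error is 0.145 under the null and 0.135 under the alternative, so z = (0.357 - 1.96 x 0.145)/0.135 = 0.53 and power is about 70%.

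**Small changes under B.** Of patients engaged under B with no true shift, 1-2% changed by less than 0.1 SD and 6-14% by less than 0.25 SD. With the 0.90 SD shift these fall below 0.5% and to at most 3%.

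**The case against.** The strongest reply is that Aim 1 already says CPM should rise, so nobody would score -10 to -14 as engaged. On that view B is the natural reading, and B separates the arms almost as well as an absolute cut-off. Much of this stands. The largest figures above (patients engaged while worse, low power) need Reading A, against which the stated direction speaks. Under B the near-zero problem is real but small. What remains is that knowing the direction does not say what to divide by when the baseline is -10 or 0, and Aim 3 writes no formula.

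A reader might infer four stronger things that the documents do not support.

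- That change in either direction counts. This would label 72-85% of unchanged patients engaged (41.7% negative, r = 0.4-0.8), but Aims 1 and 2 state directions, so it is the least plausible reading.
- That TSPS and SICI fail equally. No rate of zero or negative TSPS is given, and Section VII describes the stimulus train as "by being suitable for eliciting TSPS in most subjects", so the problem there is one of principle. SICI is affected only if it is scored as percent inhibition, which can be zero or negative.
- That the baseline is wholly open. Visit 1.1 is where patients are randomised, and Section VII calls it the baseline visit, though only for a medication form. Visits 1.3 and 2 fall after randomisation, and visit 1.3 has no TMS or EEG. If the visits are treated as interchangeable, switching visit reclassifies 20-35% of patients under B and 24-31% under the cut-off. That is a reason to name the visit, not an argument against the 30% rule.
- That the primary result is at risk. It uses continuous change in a mixed model.

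It is also fair that 41.7% comes from a cited study whose CPM procedure may differ, and that Section VIII does not tie 0.90 to CPM.

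**Conclusion.** The point holds in limited form. For CPM, Aim 3's rule is not fully defined as written. Taken literally it misclassifies patients with a negative baseline; taken in the stated direction it is still undefined at zero and lenient close to it. To call it an invalid measure would go too far, because Reading B is workable apart from those two faults.

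The two readings disagree in 31-40% of patients, or 17-21% at the lower rate of negative baselines. These ranges rest on normality, the assumed correlations and the cited facilitation rates; they show scale and are not estimates for this trial. The worked examples need none of these assumptions.

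The damage is confined to Aim 3's engagement count. The primary mixed model, the other continuous analyses and the sample size are unaffected. The change should be made, but it is not critical. Confidence is medium, because figures and pages that cannot be read in Sections II and VIII and in the visit schedule could contain a definition. If they do, the sponsor need only point to it.

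**What to change.** Before unblinding, add a few sentences to Aim 3 and Section VIII:

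- For CPM and TSPS, define engagement as a change in the hypothesised direction (CPM up, TSPS down) of at least 0.30 x |baseline| and also at least one prespecified minimum in rating points. A directed absolute threshold alone would also do. Either is defined at zero and removes trivial changes.
- The sponsor should choose and justify the minimum. Half the blinded pooled baseline SD is one example. It has no source in the documents, and in the simulation it still labels 21-32% of unchanged patients engaged. At that value the combined rule and the plain cut-off differ in at most 2.0% of simulated patients.
- Name visit 1.1 as the baseline, and state that its assessment precedes the group-specific conditioning exercise.
- Keep the plain 30% rule, with direction stated, only for strictly positive markers such as theta power or SICI as a conditioned-to-test MEP ratio. If SICI is scored as percent inhibition, use a directed absolute threshold.

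No new data are needed. The cost is that the simple 30% label is lost or qualified for these markers, and that a threshold has to be defended.
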